## I. Hypotheses and Specific Aims:

Karyotype 47,XXY, also known as Klinefelter syndrome, is the most common chromosomal abnormality in boys, affecting 1/600 male births or nearly 6 million individuals worldwide. XXY is associated with testosterone (T) deficiency from primary testicular failure, motor and neurocognitive deficits, and cardiometabolic disorders. Men with XXY have higher mortality, with cardiovascular disease being the leading cause of death (standardized mortality ratio 5.8). An essential question in XXY is whether the observed phenotype is solely attributable to the gene dosage effect from the extra X chromosome, or whether T insufficiency contributes to the neurocognitive deficits and metabolic dysfunction and therefore could be mitigated by T treatment.

The hypothalamic-pituitary-gonadal axis is activated twice in post-natal life: the mini-puberty period of infancy and true puberty early in the second decade. Although understudied, the T surge of mini-puberty in the first few months of life may play a role in long-term metabolic programming of energy metabolism and neurocognition. Infants with XXY have a blunted T surge and giving T to infants with XXY has recently been proposed as an intervention. However, the only data to support this practice are retrospective reports of better cognitive scores in XXY boys who had received T in infancy. With the rapidly increasing rate of XXY diagnoses from non-invasive prenatal testing, it is crucial to study the efficacy and safety of infant T in XXY now. Recognizing this clinical equipoise, we conducted a pilot study to evaluate body composition (a surrogate marker of cardiometabolic health) as a short-term outcome of T treatment. Building on these preliminary results, we propose further studying the short-term effects of T on cardiometabolic and developmental outcomes. Our central hypothesis is that T treatment positively influences cardiometabolic and neurodevelopmental outcomes in XXY infants (Figure 1). To test this hypothesis, we will undertake the following specific aims.

### Specific Aim 1: To quantify the short-term effect of T in infants with XXY on cardiometabolic outcomes.

**Hypothesis:** Percent body fat (%BF) will follow a normal trajectory in treated infants, while infants not receiving T will have greater %BF. **Approach:** In the TESTO: Testosterone Effects on Short-Term Outcomes trial, infants with XXY (n=75) age 4-12 weeks will be randomized 1:1 to receive 25mg intramuscular T injections every 4 weeks for 3 doses or placebo. %BF will be assessed by air displacement plethysmography at baseline, 12 weeks, and 24 weeks. The primary outcome is change in %BF z-scores at 12 weeks between groups (powered to detect a difference of 0.5SD). Infants initially receiving placebo will get T in the second half of the study (12-24 weeks). Secondary outcomes include change %BF z-scores from 12-24 weeks, growth parameters, and serum leptin.

**Specific Aim 2: To quantify the short-term effects of T in infants with XXY on neurodevelopment, gonadal function and safety outcomes.**

**Hypothesis:** (1): XXY infants receiving T will have greater gains in standard scores on early motor skills, emerging language, and adaptive functioning. (2): T treatment will not impair gonadal function, as measured by gonadotropins and biomarkers of Sertoli cell function. (3): There will be no serious adverse outcomes associated with T treatment in infants with XXY. **Approach:** Infants from Aim 1 will be given standardized neurodevelopment assessments at baseline, 12 and 24 weeks. Serum hormone biomarkers of gonadal function will also be obtained at these times. Adverse events will be monitored throughout the study.

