### B. Description of Population to be Enrolled:

A total of 75 infants with XXY will be enrolled. We will include all races, ethnicities, and languages.

*Inclusion criteria:* Male infants with 47,XXY karyotype identified prenatally who are 4-12 weeks old (31 to 90 days of age). 47,XXY must be from a diagnostic test such as CVS, amniocentesis, or post-natal blood/tissue. Non-invasive prenatal screening results alone will not be accepted.

*Exclusion criteria:*

- 1) >20% mosaicism for a normal cell line
- 2) Gestational age at birth <36 weeks
- 3) Birth weight <2.5thile or >97.5thile for age (small or large for gestational age)
- 4) History of thrombosis in self or a first degree relative
- 5) Exposure to androgen therapy outside the study protocol
- 6) Use of medications known to affect body composition, such as growth hormone or insulin
- 7) Known allergy to the testosterone cypionate solution components including benyl benzoate, benzyl alcohol, or cottonseed oil

Involving children is imperative as boys <18 years of age with XXY are much a different population than adult men with XXY. Men with XXY have been shown to have a high prevalence of type 2 diabetes, metabolic syndrome, fatty liver disease, and psychosocial difficulties. Clearly these processes begin in childhood. The potential to intervene in a preventative fashion, prior to the onset of disease, is more promising and productive than trying to treat pre-existing disease. Infant boys are exposed to endogenous testosterone in the first few months of life known as the “mini-puberty period of infancy.” Animal and human studies suggest this is a critical period for biologic programming, and therefore cannot be replicated at any other point in life. Including children in this study design allows us to investigate testosterone as a targeted intervention at this critical time point with evaluation of early markers of disease and disability. The ultimate goal is to improve the lives of children and adults with this condition.

The age of the infants at enrollment was chosen 1) to allow assessment of testicular function during the expected mini-puberty period of infancy, 2) to assure visits 2 and 3 will be completed before the infant is 10kg, as this is the upper weight limit for the PeaPod (our body composition assessment tool), and 3) feedback from parents.

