**3. VENIPUNCTURE.** Venous blood samples will be drawn in the morning a minimum of 180 minutes after eating (fasting for an infant.) The collection of blood samples may result in temporary discomfort, bruising, bleeding, and on rare occasions, infection. Standard hospital precautions for venipuncture will be followed. Anemia is also a risk; the routine guidelines in our Pediatric CTSC are 2.5 ml/kg per blood draw. We will draw 8 ml of blood per visit. If the subject is <3.2kg on the first visit we will reduce the amount of blood to be drawn.

*Likelihood of experiencing any risk: moderate (temporary discomfort).*

*Likelihood of experiencing serious risk: very low*

**Hormones.** Serum will be processed and stored at -80 degrees until batch analysis for quantification of LH, FSH, total and free T by liquid chromatography tandem mass spectroscopy (LC/MS), AMH, INHB, estradiol and leptin. Serum testosterone, inhibin B, AMH, estradiol and gonadotropins at baseline will allow us to assess endogenous testicular function. Hormone concentrations after testosterone exposure will serve as a short-term safety measure of testicular function. Exploratory aims may include looking at whether baseline serum testosterone predicts change in our outcomes after testosterone exposure. Leptin is biomarker of adiposity and will be used as a secondary measure to support our Peapod findings. Our previous work has shown that leptin concentrations are higher in boys with Klinefelter syndrome and this study will be the first to assess this in infants and explore how testosterone supplementation alters leptin in this population. Finally, we will measure serum lipids (triglycerides and HDL) and insulin as markers of insulin resistance using Trig/HDL ratio and 1/insulin as estimates. There are very limited validated assessments of cardiometabolic health in infants, therefore these data will largely be exploratory. If blood volume is limited, the order of priority for serum measurements will be as follows: Testosterone > inhibin B > leptin > gonadotropins > AMH > lipids > insulin > estradiol. Additional serum may be saved for future analyses.

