**F. Data Analysis Plan:**

The primary outcome for **specific aim 1** is the change in %BF z-scores between baseline and 12 weeks between treatment groups. Z-scores will be calculated using published norms for age, and the difference between groups will be assessed with a two-sided t-test using an alpha of 0.05. Allowing for a 10% drop-out rate, a sample size of 27 in each group gives us 80% power to detect a difference down to 0.5 z-score change between groups, and >99% power to detect the change score we observed in our pilot study (1.0 z-score change) assuming a variance of 0.65 per our pilot data. We will next use regression models with treatment group, baseline %BF, age of enrollment and feeding method as explanatory variables to assess absolute %BF at 12 weeks. Secondary analyses will include change in %BF z-scores from 12 to 24 weeks 1) in the group receiving T first (are the effects of T maintained or lost?) and 2) in the group receiving T second (does later T have the same effect?). We will analyze anthropometric measurements and serum biomarkers similarly.

For **specific aim 2**, the change in standard scores on developmental assessments will be analyzed in a similar fashion as in specific aim 1. Based on our pilot data, our sample size will yield 80% power to detect a difference between groups of 23 percentile points on the AIMS composite. Secondary analysis will include the changes in scaled scores for the individual Peabody domains and AIMS subtests, the Bayley composite scores, and the ABAS composite at 12 and 24 weeks. Gonadal function and safety outcomes will be compared between subjects on T and placebo using descriptive statistics.

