### G. Summarize Knowledge to be Gained:

This will be the largest assessment of cardiometabolic health, neurodevelopment and testicular function biomarkers in infants with XXY to date and the only longitudinal or interventional study. Management of KS in infancy and childhood is particularly important as screening for fetal aneuploidy is becoming standard of care in all pregnancies through non-invasive prenatal testing. Thousands more infants will be diagnosed with KS with very limited evidence-based management guidelines currently available. Providers and parents alike are seeking more information and options to prevent complications and co-morbidities in this condition. Our results will inform the clinical management of testosterone therapy in infants with XXY, with the promise to provide an early intervention during a critical period that may prevent cardiometabolic and neurodevelopment deficits. If testosterone therapy positively effects body composition and development in infants and does not have safety issues, there would be support for giving this therapy as well as doing long-term follow-up studies. If no short-term benefits are shown following testosterone administration, this would provide evidence for not treating these infants. This study also sets up a unique opportunity to evaluate changes in the metabolome in response to exogenous testosterone, revealing underlying mechanisms involved in the regulation of metabolism and neurodevelopmental pathways during a critical period of infancy.

Furthermore, results of this work may be generalizable beyond KS in understanding the understudied relationship of hypogonadism, body composition, and insulin resistance characteristic of obese boys, a problem of increasing significance secondary to the pediatric obesity epidemic. Other hypogonadal populations including Turner syndrome, Prader-Willi syndrome, and Down syndrome, will also benefit from the results of this study as they too have a blunted mini-puberty period of infancy.

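### The two no-harm hypotheses in Aim 2 are analysed only descriptively, with no effect estimate or interval to show how much harm the data exclude

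*Combined protocol and SAP*

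**What the plan says.** Section I, Specific Aim 2, lists three hypotheses. The second is "T treatment will not impair gonadal function, as measured by gonadotropins and biomarkers of Sertoli cell function" and the third is "There will be no serious adverse outcomes associated with T treatment in infants with XXY". Section IV.D gives the hormone assays a matching role: "Hormone concentrations after testosterone exposure will serve as a short-term safety measure of testicular function".

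The only analysis text for these two hypotheses is one sentence in the Aim 2 paragraph of section IV.F: "Gonadal function and safety outcomes will be compared between subjects on T and placebo using descriptive statistics". No section names an effect measure, an interval, a definition of impairment, a lead biomarker or a serious event rate to be excluded. The efficacy hypothesis of the same aim does get a two-group analysis and a stated detectable difference of 23 AIMS percentile points.

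Section IV.G then says how the results would be used. If T improves body composition and development and "does not have safety issues, there would be support for giving this therapy", along with longer follow-up studies.

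**The concern.** A claim that harm is absent needs a statement of how much harm remains possible. Two sets of group summaries do not give that. Means that look alike, or an empty table of serious events, can sit with quite different true effects, and the reader cannot tell which of these the data rule out.

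This goes further than routine descriptive safety tables. No harm is written here as a hypothesis, and section IV.G makes it one of the conditions for supporting treatment. No other rule in the protocol defines a safety issue: section IV.C leaves the DSMB without predetermined criteria. At stake is how the safety conclusion can be read. The primary analysis is unaffected.

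**Working it through.** **Sample sizes.** The documents give three. Section IV.B: "A total of 75 infants with XXY will be enrolled", which at 1:1 is 37 or 38 per arm. Figure 6: 30 per arm. Section IV.F: "Allowing for a 10% drop-out rate, a sample size of 27 in each group gives us 80% power to detect a difference down to 0.5". All three are carried through.

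**The plan's own figure first.** The only calculation that sets the size is for the primary outcome, "assessed with a two-sided t-test using an alpha of 0.05". With 0.65 used as an SD:

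n per arm = 2 × (1.960 + 0.842)² × 0.65² / 0.5² = 26.5, so 27.

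Power at 27 per arm is 80.7% by the normal formula and 79.2% by the t-test, so the stated 80% is reproduced. (Section IV.F calls 0.65 a variance, but the pilot's ±0.65 and ±0.67 in section III fit an SD.) Also 27 / 0.9 = 30 per arm, which matches Figure 6. No such calculation is given for gonadal function or safety.

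**Serious adverse events, if none is seen.** The exact upper limit is 1 − 0.05^(1/n) one-sided, or 1 − 0.025^(1/n) as the upper end of a two-sided 95% interval.

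| Infants on T | n | One-sided 95% | Two-sided 95% |
|---|---|---|---|
| Concurrent arm, weeks 0–12 | 27 | 10.5% | 12.8% |
| | 30 | 9.5% | 11.6% |
| | 37 | 7.8% | 9.5% |
| | 38 | 7.6% | 9.3% |
| All T-exposed, both periods | 54 | 5.4% | 6.6% |
| | 60 | 4.9% | 6.0% |
| | 75 | 3.9% | 4.8% |

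Seen the other way, a true 5% rate would give no event in 27 infants with probability 0.95^27 = 0.25. In 75 infants the probability is 0.95^75 = 0.02.

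**Gonadal markers at week 12.** The documents give no hormone SDs, so precision is shown in SD units. The half-width of an unadjusted 95% CI is t(0.975, 2n − 2) × √(2/n):

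- n = 27: 2.007 × 0.272 = 0.55 SD
- n = 30: 2.002 × 0.258 = 0.52 SD
- n = 37: 1.993 × 0.232 = 0.46 SD

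If the true difference were zero, the smallest impairment excluded with 80% power (one-sided alpha 0.025) would be 0.78, 0.74 and 0.66 SD respectively. Excluding 0.5 SD would need 2 × (1.960 + 0.842)² / 0.5² = 62.8, so 63 evaluable infants per arm.

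**Is an interval supplied elsewhere?** Section IV.F says that serum biomarkers will be handled like the primary outcome. That sentence closes the Aim 1 paragraph. Table 2 lists leptin, lipids and insulin under Aim 1, and LH, FSH, INHB, AMH, E2 and total T under Aim 2. The explicit Aim 2 sentence therefore governs the gonadal markers.

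**The case against.** Several stronger readings are tempting, and the documents do not support them.

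- **That the arms will not be compared.** Section IV.F does plan a comparison between T and placebo. What it leaves open is the form of that comparison and whether an interval will be given. The phrase could cover an interval, but nothing commits to one.
- **That similar means or zero events will be taken as proof of safety.** No section states such a rule. Section IV.G also requires efficacy and looks ahead to long-term follow-up. Section IV.C says that the effect on later fertility is unknown, and section IV.D calls the hormones a short-term measure.
- **That a serious event rate near 10% is the headline.** That figure applies to the concurrent T arm at the smaller sizes. Every infant is scheduled to receive T, so the rate among all exposed infants is bounded more tightly, at 3.9% to 5.4%. Section IV.E says that weeks 12–24 have no control group. This limits attribution but does not prevent estimating the rate.
- **That the trial is too small for any conclusion about gonadal function.** Impairments of about 0.66 to 0.78 SD could be excluded with 80% power. The gap is the missing interval and definition of impairment, more than the number of infants.

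It is also fair to say that Aim 2 is titled as quantification, that these outcomes are secondary, that the DSMB reviews adverse events and testicular function, and that descriptive reporting of serious events is usual in a trial of this size. These points lower the stakes. They do not supply the missing estimate.

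**Conclusion.** The point holds as a gap in the specified analysis. Hypotheses (2) and (3) are no-harm claims with a stated role in the trial's conclusion, and the plan commits to nothing that measures the harm left open.

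The size depends on which of the protocol's sample sizes applies. The event limits assume that no serious event is observed; any event would raise them. The hormone half-widths assume an assay result for every evaluable infant, but section IV.D ranks gonadotropins and AMH below other assays when blood is short, so their intervals could be wider. Baseline adjustment may narrow them by an amount that the documents do not allow one to estimate. With neither hormone SDs nor a margin given, the clinical meaning of 0.46 to 0.55 SD cannot be stated, and calling it a sizeable impairment would go beyond the documents.

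**What to change.** In section IV.F:

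1. For the gonadal markers, replace the descriptive wording with: *week-12 between-arm difference in INHB, AMH, LH and FSH (log scale, adjusted for baseline) with 95% CI*.
2. State for each marker which direction counts as impairment. Section II describes testicular failure in adults as raised gonadotropins with low testicular hormones, so the direction may differ between LH/FSH and INHB/AMH. The investigators need to say what applies at week 12, four weeks after the third injection.
3. Report serious adverse events as number, rate and exact 95% CI by arm for weeks 0–12. Report them separately for all T-exposed infants, noting that the second period has no untreated control.

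In section I, word hypotheses (2) and (3) as estimation aims. In section IV.G, limit the safety conclusion to the harm that the intervals exclude. No margin has to be agreed for this.

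The cost is wording and a few lines of analysis on data already planned, with no added visits or samples. The safety statement becomes less favourable, and the primary analysis does not change.

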**Specific Aim 3 (exploratory): To measure metabolite changes induced by T in infants with XXY.**

**Hypothesis:** Circulating metabolites involved in energy metabolism, specifically long chain acyl-carnitines (LCAC) and branched-chain amino acids (BCAA), will be lower due to improved mitochondrial function in T treated boys; T will favorably alter pathways involved in energy metabolism. **Approach:** LCAC and BCAA will be quantified at baseline and 12 weeks in the first 20 subjects. An unbiased platform of over 4,000 metabolites will also be performed to identify pathways that are differentially regulated with T treatment.

[figure not shown]
Assessing short-term safety and efficacy of T treatment in infants with XXY will provide the first evidence for establishing standard of care practices, with a planned extension for long-term outcomes. These results will generate preliminary data on mechanisms of the effects of T during the critical mini-puberty period for the development of future work, such as sex steroid-induced epigenetic modifications. Mentors with expertise in neurodevelopment, cardiometabolic outcomes, metabolomics, and clinical trials will optimize career development and foster expertise in gonadal and cardiometabolic function in children with sex chromosome aneuploidies.

## II. Background and Significance:

**XXY/Klinefelter syndrome is common and the diagnosis in childhood is increasing.** An extra X chromosome is present in ~1/600 boys, therefore over 6 million boys and men worldwide are affected by this very common, but under-diagnosed, genetic condition known as XXY or Klinefelter syndrome (KS). XXY is characterized by a high degree of phenotypic heterogeneity throughout the lifespan but nearly universal testicular insufficiency and infertility in adulthood. Our knowledge of the natural history of XXY in infancy and childhood is largely limited to birth cohort studies from the 1970's and more recent cross-sectional studies limited by ascertainment bias. Historically, less than 10% of males with XXY are diagnosed before adolescence, however the rate of prenatal diagnosis is increasing exponentially as testing of free-fetal DNA in maternal blood evolves to become standard screening in prenatal care. Furthermore, there is evidence the actual incidence of XXY is increasing as well. With greater recognition in infancy and potentially increased prevalence of XXY, there is a high demand for evidence-based research, particularly investigation of early determinants that contribute to increased morbidity and decreased quality of life in this population.

**XXY results in universal testicular dysfunction and hypogonadism.** While many features of the XXY phenotype are variable, testicular dysfunction is nearly universal. In adults, this manifests as small testes, infertility, and hypergonadotropic hypogonadism (elevated gonadotropins and low testicular hormone concentrations). The Leydig cells in the testes produce testosterone (T) and insulin-like hormone 3 (INSL3), while the Sertoli cells produce inhibin B (INHB) and anti-mullerian hormone (AMH). All of these testicular hormones have been demonstrated to be lower in XXY when compared to typical males from mid-puberty through adulthood. Microscopically, the testes of men with XXY are fibrotic with rare germ cells and Leydig cell hypertrophy.

Clinical evidence of testicular insufficiency in infants with XXY includes smaller testes size, reduced penile growth over the first months of life, mild hypotonia, and a passive temperament. Testicular biopsies have shown a lower number of germ cells in infants and children with XXY, however the histological appearance of Sertoli and Leydig cells is typically normal. Five studies (total N=83) of hormones during infancy in XXY conclude activation of the pituitary-gonadal axis in the first months of life, known as the mini-puberty, does occur, however serum T is lower in XXY in the majority. The only study to quantify T concentrations with liquid chromatography/mass spectrometry (gold standard) was done by our collaborator [name]. She found 8/38 XXY infants (21%) had serum T below the normal range during the mini-puberty period, and 83% were below the median (Figure 2). In summary, many XXY infants have evidence of testosterone insufficiency.

**Testosterone insufficiency increases cardiometabolic risk, and cardiovascular disease is the leading cause of morbidity and mortality in men with XXY.** Adult men with XXY have a high prevalence of type 2 diabetes, nonalcoholic fatty liver disease and cardiac dysfunction, with a standardized mortality ratio of 5.8 from these conditions. Many precursors of these conditions, such as insulin resistance, abdominal adiposity, and vascular dysfunction, have been shown to inversely correlate with T concentrations, and it is presumed the increase in cardiovascular-related morbidity and mortality in XXY is secondary to chronic hypogonadism. In multiple populations including men with XXY, T has been shown to improve body composition – an early surrogate marker of altered metabolism associated with the development of disorders of insulin resistance. However, there is a lack of randomized controlled trials of T in XXY and observational studies suggest that late treatment of hypogonadism does not reverse existing cardiovascular disease. Furthermore, two recent studies have found evidence of high body fat and serum markers of insulin resistance in children with XXY. Therefore, to reduce cardiovascular morbidity and mortality in XXY, we need to focus on prevention of early precursors. Body composition is a particularly intriguing outcome measure as it can be assessed throughout the lifespan, has been shown to be an early and modifiable risk marker of metabolic disease, and is directly altered by T. Body composition is also a clinically meaningful outcome measure in infancy as high body fat percentage early in life may contribute to the decreased strength, endurance, and athleticism seen in XXY. A gap exists in our knowledge of body composition in infants with XXY and the effect of T on this important outcome measure.

**The testosterone surge during the mini-puberty period in the first months of life likely plays a critical role in lifelong metabolic programming.** We have known about the mini-puberty period for decades, however the purpose of this brief activation of the hypothalamic-pituitary-gonadal axis remains quite speculative. Many tissues are sexually dimorphic and exposure to T during sensitive time points is required for masculinization of these organs. Mouse models that manipulate exposure to sex steroids in the neonatal period have found that early T exposure induces epigenetic modifications and results in lifelong effects on neurocognition and energy metabolism Blocking the neonatal T surge in male mice results in higher leptin concentrations and greater fat to muscle ratio for life, while a single dose of T given to neonatal female rodents results in differential gene expression in the liver in a masculinized pattern. Exposure to T in neonatal mice also leads to decreased DNA methylation in the brain, resulting in the sexually dimorphic differences observed in brain structure and function. In humans, several studies have reported associations between T concentrations during the mini-puberty period and brain lateralization, language organization, and gender identity. These findings are particularly relevant in XXY given the high risk of neurodevelopmental impairment and cardiometabolic disease, and suggest the mini-puberty period is a critical time for intervention.

Studying tissue-specific gene expression and epigenetic modification in human infants is invasive and labor-intensive, however we can investigate circulating metabolites that reflect systemic pathway regulation. Pathways involved in energy metabolism are of specific interest in XXY. Long chain acylcarnitines (LCAC) are intermediate metabolites of fatty acid oxidation within the mitochondria. Obesity and insulin resistance are strongly associated with mitochondrial dysfunction and accumulation of LCAC. Branched chain amino acids (BCAA) also build up in the presence of mitochondrial dysfunction and are regarded as an excellent biomarker for obesity and insulin resistance. Work by one of my mentors, [name], has found that LCAC and BCAA are elevated in infants exposed to maternal obesity in utero, demonstrating abnormal metabolism from a very young age. We know maternal obesity is associated with insulin resistance in adult offspring and these metabolite differences in infancy represent the early metabolic programming that underlies childhood determinants of adult disease. This work and the work of others highlight the critical importance of *timing* of exposures on lifelong metabolic programming, and how metabolites can serve as early biomarkers of this process.

**Finally, T treatment for infants with XXY is becoming common despite a lack of scientific evidence to support this practice.** Samango-Sprouse et al reported that a cohort of boys with XXY who had received T in infancy had better neurodevelopment in early childhood. Largely because of this single study, many parents are requesting T for their XXY sons. These proactive parents are often successful in obtaining this treatment, reinforcing disparities in care without establishing if T is effective or safe in this population. A randomized and blinded trial of T is needed to fill these critical gaps and provide evidence for establishing standard of care.

In summary, testicular dysfunction is universal in XXY and likely contributes to the clinical phenotype, including abnormalities in metabolism and neurodevelopmental deficits. The mini-puberty period of infancy represents a biologically plausible time period for intervention that may not only have immediate effects, but play an important role for lifelong metabolic programming. *A gap currently exists in our understanding of short and long-term outcomes of T treatment in infants with XXY. This study will investigate short-term outcome measures of T, including cardiometabolic, neurodevelopmental, and gonadal function, as well as explore altered regulation of energy pathway metabolites as a probable mechanism underlying metabolic programming in infancy.*

**This study is novel and the time is now.** T treatment in infants with XXY has emerged as an off-label treatment in the US in the past few years, however there is no evidence to support this practice and considerable variability exists among providers. Our **extensive experience** through the extraordinaryY Kids clinic, parent support groups, and ongoing research efforts in this population has proven this is a highly motivated group of parents who strongly desire T treatment for their sons. Despite the biologic plausibility, **no study has rigorously investigated the efficacy or safety of T in infants with XXY.** We have carefully designed this study with family engagement to allow us to answer important scientific questions on the short-term effects of T while ensuring successful recruitment and retention. Our research team has the expertise and ideal environment to successfully conduct this study and advance our understanding of the efficacy and safety of this practice. Recent changes in the clinical and research environments make now the **opportune time to conduct this study:**

[figure not shown]
- Technological advances in non-invasive prenatal screening have resulted in exponentially more infants being diagnosed with XXY. The May 2016 American College of Obstetrics and Gynecology Practice Bulletin recognized cell-free fetal DNA testing is a superior screening test that can be offered in **all** pregnancies. Implementation of this guideline means **10 times as many infants will be diagnosed with XXY.** In addition, many proposed genomic-based newborn screening tools would incidentally diagnose sex chromosome aneuploidies. The demand for knowledge in infants with XXY is great.
- At the 2nd International Workshop on Klinefelter Syndrome (Germany, March 2016) the lack of randomized controlled trials of T in XXY, and the need for these studies to be conducted with patient-centered outcomes, was emphasized and nearly unanimously agreed upon by experts in KS.
- The field of metabolomics offers an opportunity to investigate the mechanisms of these changes.

The outcome measures chosen for this study are not only surrogate markers for future disease and disability, but are **meaningful patient-centered outcomes in infancy and childhood.**

- High body fat with poor muscle tone may limit an infant’s ability to engage with his environment.
- Delays in motor, language, and social development affect 75% of boys with XXY and strongly correlate with future cognition, behavior, and academic performance.
- This study will be the first to test the hypothetical mechanism demonstrated in animal models that T induces immediate metabolic and epigenetic modifications that in turn confer lifelong effects on metabolism and neurocognition.

[figure not shown]
